## 2. 8.2 SAFETY ASSESSMENTS

If a participant meets risk criteria for suicide desire at baseline, they are provided in real time, from data collectors, local and national resources (i.e. 1-800-SUICIDE, 988, local crisis center, G-CAL, etc.). If they remain at heightened risk over time, the PI and research team will communicate that to the senior center case manager assigned to their case.

## 3. 8.3 ADVERSE EVENTS AND SERIOUS ADVERSE EVENTS

### 1. 8.3.1 DEFINITION OF ADVERSE EVENTS

This protocol uses the definition of adverse event from 21 CFR 312.32 (a): any untoward medical occurrence associated with the use of an intervention in humans, whether or not considered intervention-related.

### 2. 8.3.2 DEFINITION OF SERIOUS ADVERSE EVENTS

*Refer to your institutional review board for the latest guidance and definition of Serious Adverse Events (SAE). In some cases, it may be appropriate to create a list of expected events that do not need to be reported to the IRB.*

### 3. 8.3.3 CLASSIFICATION OF AN ADVERSE EVENT

#### 1. 8.3.3.1 SEVERITY OF EVENT

All adverse events will be assessed by the Principal Investigator, [name], and if necessary one of the two Co-PIs, Drs. [name] or [name]. For any adverse events (AEs) not included in the protocol, the following guidelines will be used to describe severity.

- **Mild** – Events require minimal or no treatment and do not interfere with the participant's daily activities (i.e. daily life stressor, etc.).
- **Moderate** – Events result in a low level of inconvenience or concern with the therapeutic measures. Moderate events may cause some interference with functioning (i.e. illness, new diagnosis, etc.).
- **Severe** – Events interrupt a participant's usual daily activity, potentially life-threatening or incapacitating (i.e. medical hospitalization, death, etc.)

#### 2. 8.3.3.2 RELATIONSHIP TO STUDY INTERVENTION/EXPERIMENTAL MANIPULATION

Based on the NIH Protocol Template for Behavioral and Social Sciences Research

All adverse events (AEs) will have their relationship to study procedures, including the intervention, assessed by an appropriately-trained clinician/researcher. The degree of certainty about causality will be graded using the categories below.

- **Related** – The adverse event is known to occur with the study procedures, there is a reasonable possibility that the study procedures caused the adverse event, or there is a temporal relationship between the study procedures and the event. Reasonable possibility means that there is evidence to suggest a causal relationship between the study procedures and the adverse event.
- **Not Related** – There is not a reasonable possibility that the study procedures caused the event, there is no temporal relationship between the study procedures and event onset, or an alternate etiology has been established.

3.

### 8.3.3.3 EXPECTEDNESS

A clinician/researcher with appropriate expertise in the treatment will be responsible for determining whether an adverse event (AE) is expected or unexpected. An AE will be considered unexpected if the nature, severity, or frequency of the event is not consistent with the risk information previously described for the study procedures.

## 4. 8.3.4 TIME PERIOD AND FREQUENCY FOR EVENT ASSESSMENT AND FOLLOW-UP

The occurrence of an adverse event (AE) or serious adverse event (SAE) may come to the attention of study personnel during the treatment, and/or data collection.

All AEs, not otherwise precluded per the protocol, will be captured on our lab tracking file. Information to be collected includes event description, time of onset, severity, relationship to study procedures, and whether or not the AE will impact the participant's ability to participate. All AEs occurring while on study will be documented appropriately regardless of relationship.

All AEs will attempt to be followed up with resolution, to the degree possible. However, in some cases, resolution may not be possible (i.e. hospitalization, death).

Data collectors will record any AEs that present during data collection, and treatment providers will record any AEs that present during treatment.

5.

### 8.3.5 ADVERSE EVENT REPORTING

There are no responsibilities of investigators for reporting of AEs outside of the study team and the clinical database with the exception of sustained suicide risk, which as previously noted will be reported to the case managers assigned to those particular older adult participants. This is noted in our MOUs with the 22 participating counties.

6.

### 8.3.6 SERIOUS ADVERSE EVENT REPORTING

In consultation with the PI, a trained member of the study team will be responsible for conducting an evaluation of a serious adverse event and shall report the results with the sponsor, and if relevant the participating AAAs (Area Agencies on Aging).

7.

### 8.3.7 REPORTING EVENTS TO PARTICIPANTS

N/A

8.

### 8.3.8 EVENTS OF SPECIAL INTEREST

N/A

9.

### 8.3.9 REPORTING OF PREGNANCY

N/A

4.

## 8.4 UNANTICIPATED PROBLEMS

1.

### 8.4.1 DEFINITION OF UNANTICIPATED PROBLEMS

This protocol uses the definition of Unanticipated Problems as defined by the Office for Human Research Protections (OHRP). OHRP considers unanticipated problems involving risks to participants or others to include, in general, any incident, experience, or outcome that meets all of the following criteria:

- Unexpected in terms of nature, severity, or frequency given (a) the research procedures that are described in the protocol-related documents, such as the Institutional Review Board (IRB)-approved research protocol and informed consent document; and (b) the characteristics of the participant population being studied;
- Related or possibly related to participation in the research (“possibly related” means there is a reasonable possibility that the incident, experience, or outcome may have been caused by the procedures involved in the research); and
- Suggests that the research places participants or others at a greater risk of harm (including physical, psychological, economic, or social harm) than was previously known or recognized.

2.

### 8.4.2 UNANTICIPATED PROBLEMS REPORTING

The Principal Investigator will report any unanticipated problems (UPs) to the Institutional Review Board (IRB) and to the sponsor.

Any UP report will include the following information:

- Grant #/IRB #
- A detailed description of the event, incident, experience, or outcome
- An explanation of the basis for determining that the event, incident, experience, or outcome represents an UP
- A description of any changes to the protocol or other corrective actions that have been taken or are proposed in response to the UP

To satisfy the requirement for prompt reporting, UPs will be reported using the following timeline:

- UPs that are serious adverse events (SAEs) will be reported to the PI's Office of Research and Compliance (IRB) within 7 days of when they arise
- If there are any deviations from the protocol, a protocol deviation form will be submitted to the Office of Research and Compliance within 7 days of the deviation
- Upon reconciliation of the deviation, the PI will provide written documentation through federal monitoring reports of any AEs and/or protocol deviations

3. PARTICIPANTS	8.4.3 REPORTING	UNANTICIPATED PROBLEMS	TO
N/A			

## 11. 9 STATISTICAL CONSIDERATIONS

### 1. 9.1 STATISTICAL HYPOTHESES

**Primary Endpoint(s):**

We hypothesize that older adults in both calling conditions will have reduced: social isolation, loneliness, depression, anxiety, mental health distress, and suicide desire; and they will have increased: social connection, social support, and well-being over time and in comparison to those in the control condition.

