## 4. 3 OBJECTIVES AND ENDPOINTS

Objective	Metric/Variable	Hypothesis/role/endpoint	Analysis
-----------	-----------------	--------------------------	----------

Validate the BE WITH innovation	Reduce loneliness, and elevated suicidality, and increase the degree to which social needs are met	Over the 8-week treatment loneliness and suicide desire (as measured by the UCLA loneliness scale, Interpersonal Needs Questionnaire) will be significantly decreased, and the variable of social needs being met (as measured by the social provisions scale) will be increased for both treatment groups	Longitudinal growth modeling
Validate the BE WITH innovation	Three treatment conditions	Those older adult participants randomly assigned to the BE or BE WITH treatment condition will demonstrate significant improvements in mental health outcomes when compared with the control group	Longitudinal growth modeling
Validate the BE WITH innovation	Risk tier	Those older adults that start the 8-week treatment at medium or high risk will have statistically significant improvements when compared with those of low risk	Longitudinal growth modeling
Validate the BE WITH innovation	Provider effects	Determine if there is variance in outcomes as a result of the provider assigned. 60 providers were trained in either BE or BE WITH and carried caseloads of older adult clients enabling the nesting of effects to determine if there are individual or group level provider effects	Multilevel modeling
Validate the BE WITH innovation	Improved quality, frequency of empathic and suicide intervention best practice behaviors by trained NS providers	An augmented version of Gould's (2013) coding protocol was developed to quantitatively behaviorally code treatment call dosages.	independent quantitative behavioral coding, double coding, 2 protocols, inter-rater agreement, coefficient kappas

The main overarching objective of the clinical trial is to validate the 8-week BE WITH warm calling program, equipping the Aging Services Network (ASN) with proven skills to reduce social isolation, loneliness, and elevated suicidality, while also promoting social support/well-being. The goal of the validation objective is to garner the evidence needed to get the first such program on the National Council on Aging's Evidence Based Registry.

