### 2. 9.2 SAMPLE SIZE DETERMINATION

To determine appropriate sample sizes, we used formulas developed for PN-RCTs with continuous outcomes and binary outcomes as well as results from a closely related study that tested the effect of the ASIST intervention with similar outcome measures. To detect an effect size of .40 with a continuous outcome, utilizing a Type I error rate of .05, power of .80, ICC of .20, and R^2 of .50 (for baseline covariate), we need 270 older adults with 30 volunteers each calling 6 older adults. For a binary outcome under the same assumptions, we would require 414-522 older adults with 46-58 volunteers for most estimates of the probability of an outcome in the treatment and control groups. Recruiting 540 older

adults (180 in each condition) and 60 volunteers (30 for each treatment condition) provides an adequate sample to evaluate major effects of interest in all proposed analyses.

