### 4. 9.4 STATISTICAL ANALYSES

#### 1. 9.4.1 GENERAL APPROACH

For descriptive statistics, categorical and continuous data will be presented percentages, means with standard deviations, and ranges. For qualitative research, procedural and interpretive rigor will be monitored and maintained with the use of particular CQR methodology such as Consensual Qualitative Research paired with odds ratio analysis to ensure that there are no demographic or treatment confounders. For inferential tests, we will use p-value at .01 and confidence intervals for statistical significance, along with effect sizes, etc. Covariates and confounders are pre-specified in the sections below. Checks of assumptions (e.g., normality) underlying statistical procedures will be performed and any corrective procedures needed and recommended by our biostatistician will be applied.

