Since the clinical trial is structured to occur in cohorts, the longitudinal multilevel modeling (growth modeling) analysis will be run after each cohort is completed. Despite early cohorts being underpowered, we find significant value in understanding if the data are trending in the expected directions, and/or if there are any issues that need to be addressed. The methodologist running the analysis will remain unblinded throughout the analysis process. There are no temporary suspension or safety findings that would prompt temporary suspension of the treatment. The frequency of monitoring the end points is daily as older adult participants are on a rolling recruitment and finishing their treatment at different points in time. There is no effect of the interim analysis on the final analysis as it is the same analysis. Type I error results when running many different types of tests, however we are running the main analysis with an underpowered sample so that we are learning and understanding as we go. The final analysis will be the same code just with all the participants across all 4 cohorts.

---

7. 9.4.7 SUB-GROUP ANALYSES

Sub-group analyses on the primary endpoints will be assessed in two ways: (a) multi-level modeling by treatment severity group (same primary analysis, conducted independently for low, medium, and high risk patients), and (b) cluster analysis to explore any potential differential treatment effects across predefined patient subgroups (e.g., age, sex, race, etc.). Interaction terms between any subgroup variables (i.e. age, sex, baseline severity) and treatment condition will be included to assess whether the trajectory of outcomes over time varied by subgroup. This approach will enable the examination of both between- and within-patient variability while accounting for repeated measures and clustering.

Since the secondary endpoints are serving as a fidelity check (i.e. trained helpers increased skills, retained skills, etc.) and were are only planning for approximately 60 trained helpers, which would be under powered, any differences in sub-groups, we imagine will be challenging to detect. Despite this,

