#### 10.1.2 STUDY DISCONTINUATION AND CLOSURE

This study may be temporarily suspended or prematurely terminated if there is sufficient reasonable cause. Written notification, documenting the reason for study suspension or termination, will be provided by the suspending or terminating party to study participants, investigator, funding agency, and regulatory authorities. If the study is prematurely terminated or suspended, the Principal Investigator (PI) will promptly inform study participants, the Institutional Review Board (IRB), and sponsor/funding agency and will provide the reason(s) for the termination or suspension. Study participants will be contacted, as applicable, and be informed of changes to study schedule.

Circumstances that may warrant termination or suspension include, but are not limited to:

- Determination of unexpected, significant, or unacceptable risk to participants
- Insufficient compliance of study staff to the protocol
- Determination that the primary endpoint has been met
- Determination of futility
- The funding that has been secured is cut early and abruptly

The study may resume once concerns about safety, protocol compliance, and data quality are addressed, and satisfy the funding agency, sponsor, IRB, or other relevant regulatory or oversight bodies.

---

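### The primary outcome family, the success rule and the significance level are not fixed, so the false-positive rate of a primary claim is undefined (about 5–16% at .01 per test if any one result counts)

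*Combined protocol and SAP*

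**What the plan says.** Different parts of the protocol describe the primary outcome differently.

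- Section 9.1, under primary endpoints, lists six constructs to fall ("We hypothesize that older adults in both calling conditions will have reduced: social isolation, loneliness, depression, anxiety, mental health distress, and suicide desire") and three to rise: social connection, social support and well-being. That makes nine, for both calling arms, over time and against control.
- Section 3 (objectives table) names three scales: the UCLA loneliness scale and the INQ, whose scores "will be significantly decreased, and the variable of social needs being met", as measured by the SPS, is to increase. A separate row covers the comparison of BE or BE WITH with control, but refers only to mental health outcomes in general.
- Section 8.1 tabulates six outcome scales: UCLA, GAD-7, PHQ-9, SPS-5, SF-12 and INQ (thwarted belongingness only).
- Section 4.1 lists eight instruments, of which SBQ-R, FAD and K6 are not in section 8.1.
- The synopsis gives about four constructs: isolation, loneliness, suicidality, and support or well-being.

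On the error rate, section 9.4.1 says "For inferential tests, we will use p-value at .01 and confidence intervals for statistical significance". Section 9.2 calculates the sample size "utilizing a Type I error rate of .05, power of .80, ICC of .20". Neither section says whether tests are one- or two-sided. Section 9.4.6 remarks that "Type I error results when running many different types of tests", but it is discussing the cohort-by-cohort analyses and sets no adjustment. Section 10.1.2 includes "Determination that the primary endpoint has been met" among the circumstances that may warrant stopping the study.

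**The concern.** Section 3 says the purpose is to gather evidence for a national registry listing, so the trial has to support a confirmatory claim. For that, the reader must know beforehand which comparisons count, how many must succeed, and at what level. Here, 6 to 18 comparisons with control could each be presented as the primary result, depending on which section is followed. The most favourable scale could be chosen after the data are seen, and nobody could show that the plan had been breached.

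The .01 in section 9.4.1 does not settle this. It is a per-test level and is not described as a multiplicity correction. It conflicts with the .05 in section 9.2, so the intended error rate for the trial as a whole is unknown. The closure criterion in section 10.1.2 has the same weakness: it cannot be applied until the primary endpoint is defined.

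**Working it through.** **Inputs from the documents.** Two arms are compared with control. There are 3 outcomes (section 3), 6 (section 8.1) or 9 (section 9.1). The per-test level is .01 (9.4.1) or .05 (9.2). Effect size .40, ICC .20, R² .50, 6 clients per volunteer, 180 per arm and 30 volunteers per calling arm come from 9.2.

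**Assumptions.** Tests are two-sided. Correlation between outcomes is not stated, so I use 0 to .7, with .9 as an extreme. One test is counted per outcome per arm, at the final analysis only. Section 9.4.2 describes both a baseline-adjusted post-intervention comparison and longitudinal trends; if both were tested, the count would be higher.

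**The plan's own figure.** For K volunteers in a calling arm against 6K controls:

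Var = (1 − R²) × [ (ICC/(1 − ICC))/K + 1/(6K) + 1/(6K) ]

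- K = 15: .5 × (.25/15 + 1/90 + 1/90) = .01944, SE = .1394. Power = Φ(.40/.1394 − 1.96) = .818.
- K = 14: power = .791, below .80.

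So K = 15 per calling arm, and 15 × 6 × 3 arms = 270 with 30 volunteers, as section 9.2 states. The sample size is a single-test, two-sided .05 calculation, with nothing in it for multiple outcomes.

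**False positives, independent tests.** Chance of at least one significant result when nothing works = 1 − (1 − α)^n.

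- α = .01: n = 6 gives 1 − .99^6 = 5.9%; n = 12 gives 11.4%; n = 18 gives 16.5%.
- α = .05: 26.5%, 46.0% and 60.3%.

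**Allowing for correlation.** The two contrasts share a control arm. With a design effect of 1 + 5 × .20 = 2 in the calling arm only, their correlation is 1/(2 + 1) = 1/3. Simulating correlated z statistics (400,000 draws) gives:

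| Outcomes × arms | .01, correlation .7 to 0 | of which favouring treatment | .01, correlation .9 | .05, correlation .7 to 0 |
|---|---|---|---|---|
| 3 × 2 | 4.6–5.7% | 2.3–2.9% | 3.6% | 20–26% |
| 6 × 2 | 7.4–11.2% | 3.7–5.7% | 4.9% | 29–45% |
| 9 × 2 | 9.6–16.3% | 4.8–8.5% | 5.7% | 35–59% |

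The favourable column counts results significant at two-sided .01 in the direction of benefit. A contrast correlation of .5 instead of 1/3 lowers the .01 figures by well under one percentage point.

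**The opposite success rule.** If every outcome in both arms had to be significant, the chance of a false claim could not exceed the level of one test, .01.

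**Power under the proposed rule.** Holm on six tests at .05 starts at .05/6 = .0083. At 180 per arm (K = 30), before attrition, SE = √(.5 × (.25/30 + 1/180 + 1/180)) = .0986. Then:

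- at .01: Φ(.40/.0986 − 2.576) = .931
- at .0083: Φ(.40/.0986 − 2.638) = .922

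Other readings of the variance: design effect in the calling arm only, .965 to .959; design effect in both arms, .889 to .876; R² acting only within volunteers, .793 to .775.

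**The case against.** The strongest reply is that the stricter .01 already does most of the work. With the three section 3 scales it holds the family at no more than 5.9%, close to the .05 in section 9.2. That stands, and it means that naming the family matters more than the choice of correction. It does not rescue the plan as written: .01 per test keeps independent tests within .05 only up to five (1 − .99^5 = 4.9%), and sections 8.1 and 9.1 allow 12 to 18.

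It can also be said that section 9.1 is worded as a conjunction, so that everything must improve. The text permits that reading without stating it. The any-one rule is my assumption and is likewise neither stated nor excluded. The hypotheses are directional, so false findings of benefit are only about half of the two-sided figures. Strong correlation is plausible too: section 8.1 itself reports that thwarted belongingness correlates with loneliness and low social support.

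A reader might infer several stronger points that the documents do not support.

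- *That an error rate of 7–16% applies however many scales are primary.* With three it is about 5–6%.
- *That nine scales will be tested.* Section 9.1 lists nine constructs; social isolation, mental health distress and social connection have no separate scale in section 8.1.
- *That the cohort-by-cohort analyses multiply the rate further.* Section 9.4.6 presents them as checks on trends and takes the final analysis from all participants. Whether they need control is a separate question.
- *That the trial will stop as soon as one scale is significant.* Section 10.1.2 lists circumstances that may warrant closure and gives no statistical trigger.

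**Conclusion.** The point holds as a failure to define the primary outcome family, the success rule and the governing significance level. It does not show that a particular error rate is built into the trial. The same text is compatible with a false-positive chance of at most 1% (all must succeed), of about 5–6% to 10–16% (any of three to nine outcomes at .01), or of about 20–59% (any of them at .05). The last two ranges rest on the any-one rule, two-sided tests, one final analysis and outcome correlations of 0 to .7. At a correlation of .9 the .01 figures fall to about 3.5–6%. The sample size is not in dispute: 270 reproduces, and 540 leaves room for a stricter level. This is a should-fix, since a registry claim cannot be judged until the three elements are settled.

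**What to change.** 1. In 9.1 and 9.4.2, name one primary family and use it consistently in the synopsis and sections 3 and 4.1. One option is the three scales in section 3 (UCLA, INQ thwarted belongingness, SPS-5), each for BE against control and BE WITH against control: six tests. The sponsor may prefer another set. These three also assign the screening risk tier in section 8.1, which should be considered in choosing.
2. Test the family with Holm at a two-sided family-wise .05, and state what counts as success, including whether one arm or one scale is enough.
3. Label all other scales secondary.
4. Amend 9.4.1 so that Holm replaces the flat .01 for the primary family, and reconcile it with the .05 in 9.2. Otherwise the two levels will still conflict.

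This changes wording only, with no new data or participants. Power per contrast at the first Holm step falls by about one to two points relative to .01, for example from .93 to .92 at an effect size of .40 and 180 per arm before attrition. The remaining scales lose primary status. The Holm steps are .0083, .01, .0125, .0167, .025 and .05, so the last four are more lenient than the present .01, and the sponsor should accept that knowingly.
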